Our goals in this study are:

- 1. To evaluate the effectiveness of surgical decompression in migraine headaches prospectively, using validated instruments, and to compare it to the effectiveness of a botulinum toxin injection protocol
 - a. Our hypothesis is that migraine surgery decreases the frequency and severity of migraine headaches significantly, as measured by

validated questionnaires, and that the reduction is greater and more sustainable than that seen with a botulinum toxin injection protocol

- 2. To determine which types of migraine headaches benefit most from surgical decompression and/or botulinum toxin injection
- 3. To identify prognostic factors for the success or failure of surgical decompression in migraine headache
 - a. These have been demonstrated in a previous study,⁹ but have not evaluated in a multi-center fashion.
- 4. To compare the long-term direct and indirect costs in patients with migraine headaches undergoing botulinum toxin A injections versus surgical decompression
 - a. We hypothesize that, over the long-term, surgical decompression is more cost-efficient than a botulinum toxin injection protocol

III. Procedures

a. Research design

This is a **prospective, multi-center** evaluation of the short, medium and long-term efficacy of surgical decompression in migraine headaches, comparing it to the efficacy of a botulinum toxin injection protocol.

b. Sample

Inclusion criteria:

-Patients with migraines related to a trigger site at the location of a branch of a cranial nerve (frontal, temporal, occipital)

-Patients with chronic migraine (≥15 days per month) as dictated by the FDA indication for botulinum, and as diagnosed by a board-certified neurologist

Exclusion criteria:

-Patients deemed by the senior author or the neurologist to not have migraine headaches, but an alternative diagnosis

-Patients with systemic conditions that make them poor candidates for surgery (coronary artery disease, uncontrolled diabetes mellitus, etc...)

-Patients with migraines related to inferior turbinate hypertrophy or septal deviation -Patients with a frontal, temporal or occipital trigger point who do not respond to a diagnostic botulinum toxin injection

-Hypersensitivity to any botulinum toxin preparation or to any of the components in the formulation

-Infection at the proposed injection site for botulinum

Sample size (power analysis)

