A neurologist will evaluate patients presenting for evaluation for treatment of migraine headaches, for confirmation of the diagnosis of migraine. The type of migraine that they suffer from will be recorded. If the diagnosis of migraine is confirmed, they will sign an informed consent form, and they will be asked to complete a daily headache diary, and keep track of their 1) daily use of medications for migraines, 2) physician visits for migraines, 3) ER visits for migraines, 4) days of work lost due to migraines, 5) other costs directly related to migraines for 2 months. They will also be asked to

complete three questionnaires: the Migraine Work and Productivity Loss Questionnaire (MWPLQ),¹¹ the Migraine Disability Assessment questionnaire (MIDAS)¹² and the Migraine-Specific Quality of Life questionnaire (MSQ) at the time of enrollment.

All patients will undergo a history and physical examination, including an intranasal examination. This will include determination of the possible trigger site: frontal, temporal, occipital, and inferior turbinate/septum. The trigger site can be determined using a combination of three methods: 1) Physical examination, 2) Diagnostic botulinum toxin injection into a specific trigger point, and 3) Nerve block using a local anesthetic injected into a specific trigger point in patients having active symptoms.

The patients will be asked whether they prefer to undergo surgical decompression or a botulinum toxin protocol, and their preference will be recorded.

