50 patients who prefer surgery, and who satisfy the inclusion and exclusion criteria, will be included in the study as **Group A**. The location of the trigger site(s) will be determined based on history, physical examination, a diagnostic botulinum toxin injection and/or a nerve block. If those patients are found to have a trigger site that responds to botulinum injection, they will undergo surgical decompression of their trigger site, as described in Janis *et al*⁶ and Guyuron *et al*.⁷ Those patients will be followed postoperatively. They will be asked to continue tracking their 1) daily use of medications for migraines, 2) physician visits for migraines, 3) ER visits for migraines, 4) days of work lost due to migraines, and 5) other costs directly related to migraines for 2 months. At 1 year, 2 years and 2.5 years postoperatively, they will be asked to fill the Migraine Work and Productivity Loss Questionnaire (MWPLQ), the Migraine Disability Assessment questionnaire (MIDAS) and the Migraine-Specific Quality of Life questionnaire (MSQ) again. They will also be examined by a board-certified neurologist at 1 year postoperatively.

A separate sample of 50 patients from the pool of patients undergoing the botulinum toxin injection protocol will be selected (Group B). Those patients will be matched to the individual patients in group A based on gender, age (in 5 year intervals), migraine severity (based on the Migraine Disability Assessment questionnaire, 5 –point intervals) and trigger site (pair-matching). For example, for a patient in Group A who is a 47 year-old woman with temporal migraines and a MIDAS severity score of 14, a patient on the botulinum injection protocol will be included in Group B is she is a 45 to 50 year old female with temporal migraines and a MIDAS severity score of 10 to 15.

The patients in group B will receive the botulinum injection protocol, and will continue to track their 1) daily use of medications for migraines, 2) physician visits for migraines, 3) ER visits for migraines, 4) days of work lost due to migraines, and 5) other costs directly related to migraines for 2 months. At 1 year, 2 years and 2.5 years after the start of the protocol, they will be asked to fill the Migraine Work and Productivity Loss Questionnaire (MWPLQ), the Migraine Disability Assessment questionnaire (MIDAS)

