and the Migraine-Specific Quality of Life questionnaire (MSQ). They will also be examined by a board-certified neurologist at 1 year postoperatively.

The Botox injections and the surgeries are being done as part of the routine clinical care for the patients enrolled in the study. The only procedures being done solely for research purposes are having the patients fill out the surveys and diaries.

d. Measurements

The measurements will include

- 1) Number of migraine headaches per 30 days
- 2) Cost of migraine-related medications, physician visits, ER visits
- 3) Cost of days of work lost due to migraine as calculated from the Migraine Work and Productivity Loss Questionnaire (MWPLQ)
- Score on the Migraine Disability Assessment Questionnaire (MIDAS) (0-21)
- 5) Scores on the emotional, restrictive and preventive portions of the Migraine-Specific Quality of Life questionnaire (MSQ)

The following comparisons will be made for the above measurements:

-Within Group A, compare all measurements before surgery to 1 year, 2 years and 2.5 years after surgery, using a t-test

-Within Group B, compare all measurements before start of injection protocol to 1 year, 2 years and 2.5 years after injection protocol, using a t-test

-Compare all measurements between Group A and Group B using a paired t-test analysis

e. Internal validity

The study avoids confounding by virtue of the matched-pair analysis. The study avoids recall bias by having the patients fill-out the questionnaires preoperatively and postoperatively, rather than having them retrospectively assess their improvement after surgery.

Blinding is very difficult in such a study. In order to avoid experimenter bias, all assessment will be made by the patients themselves, without influence by the experimenters.

The main threat to internal validity is the possible placebo effect inherent to migraine headache treatments. This may threaten the validity of the data on differences in clinical outcomes between the two groups. It will not threaten the validity of the data on financial cost

f. External validity

Because this is a multi-center trial that includes different patient populations treated by different clinicians, this study is generalizable to the general population of patients with migraines in the United States.

g. Data analysis

Group B will be selected by matching individual participants to members of Group A based on gender, age, migraine severity and migraine location.

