Prospective, Multi-Center Evaluation of the Efficacy of Migraine Surgery

Statistical Analysis Plan

IRB Approval #:2015H0024

NCT02351544

Document Date Version: February 16, 2014

Principal Investigator: [name], FACS (The Ohio State University)

Outcomes

**Outcomes modeled were: MHI, MIDAS A, MIDAS B, MIDAS Total, MSQ Sum and MWPLQ7 Total

Data Analysis

Descriptive statistics, such as frequency and percents, were displayed for sex (male or female), treatment (Botox or Surgery) and site (OSU or MGH). Descriptive statistics, such as mean, standard deviation, median, lower quartile and upper quartile, were reported for age and the patient reported outcomes with the respect to their migraine for each time point (baseline, 1 year, 2 years and 2.5 years).

Each of six outcomes were highly skewed and therefore natural logarithm was applied to each one before it was modeled. A constant of 1 was added to outcome values before applying natural log function so as to include raw values of zeros.

Linear mixed models with a random effect for patient were used to evaluate the changes in each of six outcomes between two different treatments over time with inclusion of interaction between treatment and time. These models were used given to account for correlation between repeated measurements on the same patient and to account for missing data across time points. P-values for both the main and interaction effects of time and treatment were reported for each model and Tukey's post hoc method was used to adjust for pairwise comparisons. For the ease of interpretation, raw means and SDs are presented for each time point within specific treatment.

Analyses were performed using SAS v9.4 (SAS Institute; Cary, NC; www.sas.com). Statistical significance was defined as two-sided alpha<0.05.

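### The SAP tests no cost: the protocol's cost of lost work days is represented only by an undefined MWPLQ7 Total on a log scale, and direct cost is absent as well

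*Protocol*

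**What the plan says.** **Protocol**

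- II Objectives, goal 4: "To compare the long-term direct and indirect costs in patients with migraine headaches undergoing botulinum toxin A injections versus surgical decompression". The attached hypothesis is that surgery is the more cost-efficient option in the long term.
- III.d Measurements, item 2: "Cost of migraine-related medications, physician visits, ER visits". Item 3: "Cost of days of work lost due to migraine as calculated from the Migraine Work and Productivity Loss Questionnaire (MWPLQ".
- III.d, comparisons: "Compare all measurements between Group A and Group B using a paired t-test analysis". Before-and-after t-tests are planned within each group. III.g Data analysis repeats these comparisons.
- III.c Detailed study procedures: at enrolment patients "complete three questionnaires: the Migraine Work and Productivity Loss Questionnaire (MWPLQ" and two others. For Group A, "At 1 year, 2 years and 2.5 years postoperatively, they will be asked to fill the Migraine Work and Productivity Loss Questionnaire (MWPLQ"; Group B has the same schedule from the start of injections. Separately, patients track medication, physician and ER visits, lost work days and other migraine costs for 2 months at enrolment, and again for 2 months after treatment.

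**SAP**

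- Outcomes: "Outcomes modeled were: MHI, MIDAS A, MIDAS B, MIDAS Total, MSQ Sum and MWPLQ7 Total".
- Data Analysis: all six outcomes are log-transformed. "A constant of 1 was added to outcome values before applying natural log function so as to include raw values of zeros". Each then enters a linear mixed model with treatment, time and their interaction. Raw means and SDs are presented to help interpretation.

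Neither document gives a unit value for a lost work day or a rule for turning MWPLQ answers into cost.

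**The concern.** The protocol names a money amount and says it will be compared between groups. The SAP's list has one variable from the same questionnaire, with no stated unit and no link to cost, and no other variable that could carry goal 4. This is a change in the quantity analysed, not just a missing detail.

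Cost is a main question of this trial. It is one of three endpoints used for the sample size (III.b), and III.e says that placebo effects threaten the clinical comparison but not the cost data. The protocol thus treats cost as its sturdier result. A test on ln(MWPLQ7 Total + 1) cannot be added to direct costs or stated as dollars per patient. It cannot show whether lost work narrows, widens or reverses the treatment-cost difference.

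**Working it through.** **1. The two documents side by side**

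| Protocol III.d | SAP outcome |
|---|---|
| 1. Migraines per 30 days | MHI (related, not identical) |
| 2. Cost of medication, physician and ER visits | none |
| 3. Cost of lost work days, from the MWPLQ | MWPLQ7 Total, undefined, as ln(value + 1) |
| 4. MIDAS score | MIDAS A, B, Total |
| 5. MSQ portion scores | MSQ Sum |

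The two cost rows are the ones with no cost counterpart.

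**2. The plan's own cost figures (III.b)**

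Inputs: 75 Units every 3 months, $12 to $15 per Unit, surgery $8,378, follow-up 2.5 years.

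- Yearly botulinum cost: 75 × 4 × $12 = $3,600; 75 × 4 × $15 = $4,500. Both match.
- 2.5 years at the midpoint: $4,050 × 2.5 = $10,125. Matches.
- Break-even: 8,378 / 4,500 = 1.86 and 8,378 / 3,600 = 2.33 years. These match the stated 1.9 to 2.3.

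These inputs are treatment costs only. No lost-work component enters them.

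**3. How much lost work would equal the planned difference**

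Difference = 750 Units × price − $8,378. Days = difference / daily value. The documents give no wage, so $100 to $300 per day is an assumption for illustration.

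| Price per Unit | Botulinum, 2.5 years | Difference | Days at $100 | Days at $300 |
|---|---|---|---|---|
| $12 | $9,000 | $622 | 6.2 | 2.1 |
| $13.50 | $10,125 | $1,747 | 17.5 | 5.8 |
| $15 | $11,250 | $2,872 | 28.7 | 9.6 |

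For the central case, 17.5 / 30 = 0.58 and 5.8 / 30 = 0.19 days a month. A between-group difference of that size would cancel or double the planned saving. Inclusion requires headache on at least 15 days per month, so a difference of this order cannot be dismissed.

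**4. What the log scale would do if the total were days**

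Constructed example with 50 patients per group:

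- Group X: 40 lose 0 days and 10 lose 20. Mean days = 200 / 50 = 4. Mean ln(y + 1) = 10 × ln 21 / 50 = 0.61.
- Group Y: all lose 2 days. Mean days = 2. Mean ln(y + 1) = ln 3 = 1.10.

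X costs twice as much as Y and looks better on the log scale.

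A milder case assumes lognormal data with equal geometric means. The ratio of arithmetic means is exp((s₂² − s₁²) / 2). Log SDs of 1.0 and 1.2 give exp(0.22) = 1.25: a 25% cost difference with no difference on the log scale. The SAP describes its outcomes as highly skewed and allows for zeros, so the distinction is relevant here.

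**5. Time span**

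The MWPLQ is taken at four time points and the diary covers 2 months at a time. Neither gives a 30-month cost directly. Scaling a 2-month diary to 2.5 years means multiplying by 30 / 2 = 15, and no rule for this is stated.

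No corrected indirect-cost figure can be computed, because the documents give no unit value and no mean or SD for lost work.

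**The case against.** **MWPLQ7 Total is undefined, so nobody can say it is not a cost.** This stands as a limit. A reader might infer that the SAP's derivation throws the cost away, or that no patient record could yield it. The documents do not show the derivation and do not support either statement. That the variable is a questionnaire total is a reasonable inference from its name, from the SAP's description of its outcomes as patient-reported, and from the absence of a valuation step. The supportable statement is that no conversion to days or money is given. If the total does turn out to be days or dollars, the log-scale problem remains.

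**The protocol still plans untransformed t-tests on this cost, and the SAP does not withdraw them.** This is true. A reader might conclude that the trial has no cost analysis anywhere, which is too strong. But the protocol gives no value for a lost day, so its t-test cannot be run as written, and the SAP, which should settle this, is silent.

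**The raw means would expose a reversal like the one in the example.** They would if the total were days. They are descriptive, however. The p-values come from the log scale, and raw means of an unvalued total are still not costs.

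**The gap is not confined to indirect cost.** This is correct. A reader might take direct cost to be covered, or to have no data source. Neither holds: the diary records medication, physician and ER visits, and measurement 2 is missing from the SAP in the same way.

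**Conclusion.** The point holds. Goal 4 and measurement 3 call for a between-group comparison of the cost of lost work days. The SAP offers only an undefined MWPLQ variable on a log scale, with direct cost also absent. An analyst who follows the SAP produces no cost comparison.

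The mismatch affects the whole of goal 4 at all four questionnaire time points. Its possible size is shown by the 17.5 to 5.8 lost days over 30 months that equal the planned $1,747, or 6.2 to 2.1 days at the low unit price. These figures rest on the assumed $100 to $300 per day and on sample-size inputs, and are not estimates of the trial's result. The example with reversed direction is constructed and shows only what the log scale permits.

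The clinical outcomes are not affected. It should be corrected because goal 4 cannot otherwise be answered.

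**What to change.** In the SAP:

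1. Define MWPLQ7 Total: items, unit, range and recall period.
2. Add measurement 3 as a derived cost: lost work days times one pre-stated daily value, the same in both groups, with a low and a high value as sensitivity analyses. Take the days from the MWPLQ. If it does not yield days, use the diary's lost-work-day item.
3. State whether the result is cost per assessment period or is extrapolated to 2.5 years, and by what rule.
4. Compare untransformed mean cost between groups with matched pairs kept together, following the protocol's paired comparison. A bootstrap interval that resamples pairs is an option for skewness.
5. State how missing assessments are handled, since a simple paired test drops a pair when either member is missing.
6. Analyse measurement 2 alongside it, over the same period, so that direct and indirect costs can be added.
7. Keep ln(MWPLQ7 Total + 1) as a productivity outcome only, and do not report it as a cost result.

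The SAP is written in the past tense. If the cost analysis is added after the data were seen, label it supplementary. If it is not done, state that the cost part of goal 4 is not analysed.

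**Cost of the change:** SAP wording, one derived variable and one further analysis for work loss, plus the analysis of measurement 2. No new data are needed if the MWPLQ yields days. The diary fallback also uses planned data but covers only 2-month windows, and follow-up windows at 1, 2 and 2.5 years are not described. A daily value must be assumed, and the interval for mean cost will be wider than one on the log scale.

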Similarly, surgical decompression of trigger sites has previously been shown to have superior clinical outcomes to medical management, through a randomized, blinded controlled-trial performed at Case Western Reserve in 2009.⁷ Patients either received actual decompression of the trigger sites, or sham surgery (exposure and visualization of the trigger sites, without decompression). At one-year follow-up, the group who underwent actual surgery demonstrated a statistically higher proportion with significant improvement in their migraines (83.7% vs. 57.7%, p=0.014), and with complete elimination of their migraines (57.1% vs. 3.8%, p<0.001). Several other reports have confirmed the good clinical outcomes of surgery demonstrated in this trial,^{6,8} and surgical decompression is now commonly performed by several surgeons around the United States.

Prognostic factors predicting the success of surgical decompression in migraine headache treatment include older age of migraine onset, visual symptoms/aura, and 4-site decompression. Factors predicting failure of surgery include excessive operative blood loss, and surgery on only one or two trigger sites.⁹

One criticism of the studies on migraine surgery has been that most of the results have originated from the same institution (Case Western Reserve), and from the same author (Guyuron). While several studies at other institutions have demonstrated positive outcomes of migraine surgery,⁶ these have only included a small number of patients.

In addition, the sham surgery randomized-controlled trial has been criticized for not clarifying any prior treatments that patients had undergone before migraine surgery, and for not showing how medication use patterns changed after surgery. Another criticism of that study was the fact that patients were examined by neurologists before the study but not after the study, and that surgery was performed on some patients with episodic migraines, who are known to not benefit from botulinum toxin. It is unclear what migraine types are most likely to benefit from surgical decompression.

Our goal is to perform a multi-center, prospective trial to demonstrate the effectiveness of migraine surgery, which would address the criticisms mentioned above. The main aim is to demonstrate that the positive results demonstrated by Guyuron *et al* are reproducible at other institutions and by other surgeons using similar techniques on different patient populations.

II. Objectives

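### Matching on four variables does not avoid confounding when patients choose their treatment: aura and age at migraine onset, which the protocol itself calls prognostic for surgery, are neither matched nor modelled.

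*Protocol*

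**What the plan says.** Treatment is not randomised. Protocol III.c states: "The patients will be asked whether they prefer to undergo surgical decompression or a botulinum toxin protocol, and their preference will be recorded". It continues: "50 patients who prefer surgery, and who satisfy the inclusion and exclusion criteria, will be included in the study as" Group A. For Group B, a separate 50 patients "from the pool of patients undergoing the botulinum toxin injection protocol will be selected".

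III.g gives the matching: "Group B will be selected by matching individual participants to members of Group A based on gender, age, migraine severity and migraine location". III.c sets the bands at 5 years for age and 5 points for MIDAS.

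The background text, ahead of section II, states: "Prognostic factors predicting the success of surgical decompression in migraine headache treatment include older age of migraine onset, visual symptoms/aura, and 4-site decompression". It adds: "Factors predicting failure of surgery include excessive operative blood loss, and surgery on only one or two trigger sites". III.c says that the type of migraine will be recorded and that a history will be taken.

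III.d and III.g compare the groups by paired t-test and list no covariates. The SAP (Data Analysis) replaces this with linear mixed models with a random patient effect, "with inclusion of interaction between treatment and time". It names no baseline covariate and no pair term.

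III.e nevertheless concludes: "The study avoids confounding by virtue of the matched-pair analysis". The main threat it names is the placebo effect. It does not mention selection by preference.

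**The concern.** Matching balances the variables that are matched and whatever travels with them. Patients who prefer surgery may differ from those on injections in aura, migraine type or age at onset, even within a perfect four-variable match. If such a factor also affects outcome, part of the difference between groups belongs to case mix and not to treatment.

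Objective 1 is a comparative claim about surgery against botulinum toxin, so a reader will rely on III.e when interpreting that comparison. The statement also sits badly with Objectives 2 and 3, which treat migraine type and prognostic factors as open determinants of response.

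**Working it through.** **1. The plan's own figure.** The sentence in III.e carries no number. The nearest scale is the efficacy sample size in III.b: improvement in the Migraine Headache Index of 96.6% against 87.5% (difference 9.1), SD 20, alpha 5%, power 80%, stated answer 30 per group.

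- One-sided, paired, with 20 as the SD of pair differences: ((1.645 + 0.842) × 20 / 9.1)² = 29.9, so 30. This reproduces the stated figure.
- Two-sided, the same formula gives 38 pairs. Two independent groups, two-sided, give 76 per group.

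That discrepancy is a separate matter. It matters here only because the plan leaves two standard errors possible at 50 per group: 20 × √(2/50) = 4.0 (independent) or 20 / √50 = 2.83 (paired).

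**2. What is covered.**

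| Factor | Matched | Adjusted for |
|---|---|---|
| Gender, current age, MIDAS severity, trigger site | Yes | Through pairing in the t-test; no term in the SAP model |
| Aura / migraine type | No | No |
| Age at migraine onset | No (current age only) | No |
| Number of trigger sites | Unclear; site is matched, count is not mentioned | No |
| Sites operated on, operative blood loss | Cannot be; they exist only in Group A | Not baseline variables |

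The clear gaps are aura or migraine type and age at onset.

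**3. When an unmatched factor biases the comparison.** Let a binary factor have prevalence pA and pB in the two groups. Let it change mean improvement by g1 under surgery and g0 under botulinum toxin, with means m1 and m0 when it is absent.

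- Observed difference: (m1 + g1·pA) − (m0 + g0·pB).
- True effect in the Group A population: (m1 + g1·pA) − (m0 + g0·pA).
- Bias: g0 × (pA − pB).

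Bias therefore requires the factor to affect outcome under botulinum toxin. The background text speaks only to outcome after surgery (g1). The documents give neither g0 nor the prevalence gap.

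**4. Illustration with assumed inputs.** Take no treatment effect for any patient and the same factor effect in both groups. The false-positive rate at bias b is Φ(b/SE − 1.96) + Φ(−b/SE − 1.96).

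| Gap (points) | Factor effect (points) | Bias | Share of 9.1 | False positives, SE 4.0 | SE 2.83 |
|---|---|---|---|---|---|
| 10 | 10 | 1.0 | 11% | 5.7% | 6.4% |
| 10 | 20 | 2.0 | 22% | 7.9% | 10.9% |
| 30 | 10 | 3.0 | 33% | 11.7% | 18.6% |
| 20 | 20 | 4.0 | 44% | 17.0% | 29.3% |
| 30 | 20 | 6.0 | 66% | 32.3% | 56.4% |

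To produce the whole 9.1 points, the gap would have to be 9.1 / effect: 91, 46 or 30 percentage points for effects of 10, 20 or 30. In a simulation of the unpaired comparison (4,000 runs per setting), adding the factor as a covariate brought mean bias to within 0.12 of zero and the false-positive rate to 4.4–5.5%. More patients would not remove the bias.

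**5. What the SAP model already removes.** With baseline as one of the time points, the treatment-by-time term removes group differences that stay constant on the log(outcome + 1) scale. A factor that predicts how far patients improve acts on the change itself and is not removed.

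**The case against.** The strongest reply is that the background lists predictors of response among operated patients. Nothing in the documents says that they predict outcome under botulinum toxin. If aura and onset age only modify the response to surgery, g0 is zero. The comparison is then unbiased for patients who choose surgery, and imbalance affects only which population the estimate describes. This stands. It limits what can be said about size, but it does not rescue III.e: the documents do not show g0 to be zero either, and preference may bring other unmatched differences.

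Two further readings are tempting and go too far.

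- A reader might count the number of sites operated on, or blood loss, as omitted confounders. Both belong to the operation. The count of trigger sites is a baseline variable, but III.c matches on trigger site and may cover it in part.
- A reader might add baseline headache frequency to the named prognostic factors that were left out. The background does not name it. Entry requires at least 15 days per month, MIDAS is matched, and baseline is already a time point in the SAP model. Excluding patients who do not respond to a diagnostic injection narrows case mix further.

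It is also fair to say that the preference-based design is described openly and that no covariate set can remove confounding by preference. That argues for correcting the statement, since adjustment alone cannot make it true.

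**Conclusion.** The statement in III.e is not supported. Treatment follows preference, four variables are matched, and two baseline factors that the protocol itself calls prognostic for surgery are left out of both the matching and the analysis. This should be fixed. It does not invalidate the study, and it does not depend on how well the matching or the pairing is carried out.

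A reader might infer that the plan inflates the apparent benefit of surgery, or that its false-positive rate is some 12% or 32%. The documents support neither. The bias could equally hide a benefit. The rates rest on assumed gaps and on an assumed factor effect that is the same in both groups. They are also on a percent-improvement scale, whereas the SAP models log(outcome + 1). They show only that moderate imbalance could matter at 50 per group.

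**What to change.** 1. Replace the sentence in III.e with: *matching reduces confounding by gender, age, MIDAS severity and trigger site; confounding by patient preference and unmatched factors remains.* Limit the comparative conclusion to match.
2. Report baseline balance between groups, and add an adjusted version of the SAP model with a small covariate set: migraine type or aura, and age at onset. Add number of trigger sites only if pairs are not already matched on it. Each covariate needs a by-time term, because a main effect alone shifts all time points equally and leaves the treatment-by-time contrast unadjusted. Alternatively, model follow-up values adjusted for the baseline outcome, so that baseline is not both covariate and response. The SAP is written in the past tense; if outcomes have already been seen, label the adjusted model a sensitivity analysis.
3. Report how strong an unmeasured factor would have to be to explain the observed difference.

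The cost is some degrees of freedom and some data entry. With aura binary and onset age linear, the by-time model adds 2 × 4 = 8 parameters per outcome. A longer list that adds baseline headache frequency and a three-level site count would add (1 + 1 + 1 + 2) × 4 = 20, which is too many for at most 100 patients before drop-out. Migraine type is already recorded. Onset age would be entered from the history already taken, assuming that the history captures it.
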